The secondary objectives of the study are to assess the effect of dapagliflozin on 24 hour urine glucose excretion when administered once a day (10 mg) versus twice a day (5 mg every 12 hours) at steady state (after five days of dosing), the exploratory objectives to indirectly determine if dapagliflozin may inhibit the rate of gut glucose absorption by comparing the plasma glucose, insulin, ~~GLP-1~~ and GIP responses to meals accompanied with or without the administration of dapagliflozin.

[...]

Section of protocol affected:

Section 11.3, Calculation or derivation of pharmacodynamic variables, subheading Inhibition of glucose re-absorption

The following was added following the paragraph of this section:

The percent inhibition of renal glucose re-absorption during each urine collection interval will be calculated as $100 \times$ amount of glucose excreted in the urine from each 4-our interval/the amount of glucose renally filtrated from each 4-hour interval.

Section of protocol affected:

Section 11.3, Calculation or derivation of pharmacodynamic variables, subheading Inhibition of rate of gut glucose absorption

Previous text:

Inhibition of rate of gut glucose absorption

For plasma glucose insulin, GLP-1 (7-36 amide) and GIP the area under the effect time curve until 180 minutes after each meal (AUE_{0-180}) will be calculated for each subject in each period. The AUE_{0-180} will be calculated using the linear trapezoidal rule.

Revised text:

Inhibition of rate of gut glucose absorption

For plasma glucose **and** insulin, ~~GLP-1 (7-36 amide) and GIP~~ the area under the effect time curve until 180 minutes after each meal (AUE_{0-180}) will be calculated for each subject in each period. The AUE_{0-180} will be calculated using the linear trapezoidal rule.

Section of protocol affected:

Section 12.2.4, Pharmacodynamics, 4th paragraph

Previous text:

[...]

For plasma glucose, insulin, GLP-1 (7-36 amide) and GIP the area under the effect time curve until 180 minutes after each meal (AUE_{0-180}) will be calculated. Baseline adjusted geometric mean differences between both treatment groups will be estimated by a linear model on the log-transformed AUEs after each meal, and retransforming the point estimates and 95% confidence intervals. The linear model will include treatment, sequence, period as fixed effects, subjects nested within sequence as random effect and baseline concentration as continuous covariate. AUEs after each meal will be analyzed in a separate model.

Results of the analysis after dinner will be used to determine if dapagliflozin inhibits the rate of gut glucose absorption by comparing the plasma glucose, insulin, GLP-1 and GIP responses to meals accompanied with (5 mg BID) or without the administration of dapagliflozin (10 mg OD).

Revised text:

[...]

For plasma glucose **and** insulin, ~~GLP-1 (7-36 amide) and GIP~~ the area under the effect time curve until 180 minutes after each meal (AUE₀₋₁₈₀) will be calculated. Baseline adjusted geometric mean differences between both treatment groups will be estimated by a linear model on the log-transformed AUEs after each meal and retransforming the point estimates and 95% confidence intervals. The linear model will include treatment, sequence, period as fixed effects, subjects nested within sequence as random effect and baseline concentration as continuous covariate. AUEs after each meal will be analyzed in a separate model.

Differences between pre- and post-meal GIP measurements will be determined at dinner only. The change in GIP between the two study periods for each subject will be compared and statistically analyzed.

Results of the analysis after dinner will be used to determine if dapagliflozin inhibits the rate of gut glucose absorption by comparing the plasma glucose, insulin, ~~GLP-1~~ and GIP responses to meals accompanied with (5 mg BID) or without the administration of dapagliflozin (10 mg OD).

Section of protocol affected:

Section 12.2, Methods of statistical analyses

The following section was added:

12.2.5 PK/PD relationship

The average plasma concentration vs percent inhibition of glucose re-absorption or the amount of glucose excreted will be explored and the results will be reported separately if any relationship can be determined.

Section of protocol affected:

Section 12.2, Methods of statistical analyses

Previous heading number:

12.2.5, Safety and tolerability

Revised heading number:

~~12.2.5~~, **12.2.6** Safety and tolerability

Section of protocol affected:

Section 12.2, Methods of statistical analyses

Previous heading number:

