12.2 Methods of statistical analyses

12.2.1 General principles

All statistical summaries and analyses will be performed by PAREXEL International GmbH using SAS[®] 9.1.3 (SAS[®] Institute, Cary NC, USA) or the statistical package StatXact[®], version 6. Statistical and analytical procedures will be detailed in a Statistical Analysis Plan (SAP).

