12.2.4 Pharmacodynamics

The primary objective of this study is to assess the effect of twice-daily dosing versus once-daily dosing of the same total daily dose of dapagliflozin on percent inhibition of glucose re-absorption. The primary pharmacodynamic endpoint (percent inhibition of renal glucose re-absorption over 24 hours), and the secondary pharmacodynamic endpoint (total urinary glucose excretion over 24 hours) will be analyzed using an ANOVA model, with sequence, period and treatment regimen (10 mg dapagliflozin OD x 5 days versus 5 mg dapagliflozin BID x 5 days) as fixed effects and subject within sequence as a random effect. Estimated least square means and difference between treatments least squares means will be reported with 95% confidence intervals, with adjustment for other factors in the model done.

If there is after inspecting ANOVA model diagnostics convincing evidence that one or more of the model assumptions are not valid, a nonparametric analysis of the treatment regimen differences will also be reported using the Hodges-Lehmann estimator of the median difference together with a corresponding exact 95% confidence interval.

Graphical presentations will be used as appropriate. Examples may include line graphs showing individual or mean development over time.

For plasma glucose, insulin, GLP-1 (7-36 amide) and GIP the area under the effect time curve until 180 minutes after each meal (AUE_{0-180}) will be calculated. Baseline adjusted geometric mean differences between both treatment groups will be estimated by a linear model on the log-transformed AUEs after each meal and retransforming the point estimates and 95% confidence intervals. The linear model will include treatment, sequence, period as fixed effects, subjects nested within sequence as random effect and baseline concentration as continuous covariate. AUEs after each meal will be analyzed in a separate model.

Results of the analysis after dinner will be used to determine if dapagliflozin inhibits the rate of gut glucose absorption by comparing the plasma glucose, insulin, GLP-1 and GIP responses to meals accompanied with (5 mg BID) or without the administration of dapagliflozin (10 mg OD).

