12.2.6 Interim analyses (Not applicable)

12.3 Determination of sample size

If 14 subjects complete both periods of the study and if the intra-subject variance is one half the total variance observed in the 10 mg group on Day 7 for average percent inhibition of glucose re-absorption over 0-12 hours in Bristol-Myers Squibb Study MB102002 (mean/SD_{total}=24.5%/15.4%), then a 95% confidence interval for the difference between regimens in mean percent inhibition of glucose re-absorption over 24 hours (δ) is expected to be approximately $\delta \pm 9.0$ percentage points.

The sample size for this study was selected to be consistent with the research hypothesis as described in section [1.2](#).

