- To indirectly determine if dapagliflozin may inhibit the rate of gut glucose absorption by comparing the plasma glucose, insulin, ~~GLP-1 (7-36 amide)~~ (~~glucagon-like peptide~~) and GIP (glucose-dependent insulintropic polypeptide) responses to meals accompanied with or without the administration of dapagliflozin
- **To explore plasma dapagliflozin concentration vs urine glucose excretion relationship**

Section of protocol affected:

Synopsis, Outcome variables, pharmacokinetics:

Previous text:

- C_{\max} , $C_{ss,\max}$, $C_{ss,\min}$, AUC_{τ} and AUC_{ss}

[...]

For BID dosing, blood PK samples will be collected according to following schedule:

- Day 1: 0, 0.25, 0.5, 1, 1.5, 2, 3, 4, 6, 8, 12, 12.25, 12.5, 13, 13.5, 14, 15, 16, 18, 20, and 24 hours;
- Day 3 and Day 4: 0 hour (pre-dose of the morning dose);

[...]

Revised text:

Synopsis, Outcome variables, pharmacokinetics:

- C_{\max} , $C_{ss,\max}$, $C_{ss,\min}$, $C_{ss,av,t-t+4}$, AUC_{τ} and AUC_{ss}

[...]

For BID dosing, blood PK samples will be collected according to following schedule:

- Day 1: 0, 0.25, 0.5, 1, 1.5, 2, 3, 4, 6, 8; and ~~12, 12.25, 12.5, 13, 13.5, 14, 15, 16, 18, 20, and 24~~ hours;
- Day 3 and Day 4: 0 hour (pre-dose of the morning dose);

[...]

Section of protocol affected:

Synopsis, Outcome variables, Pharmacodynamics

Previous text:

- Percent inhibition of renal glucose re-absorption over 24 hours
 - Blood samples for plasma glucose will be drawn on Day 5 at 0, 1, 2, 3, 4, 5, 6, 7, 8, 9, 10, 11, 12, 13, 14, 15, 16, 18, 20, 24 hours.
 - Blood samples for creatinine will be drawn at pre-dose of Day 4 and of Day 5.
- Inhibition of rate of gut glucose absorption by determination of plasma glucose, insulin, GLP-1 (7-36 amide) (glucagon-like peptide 1) and GIP (glucose-dependent insulinotropic polypeptide)
 - Blood samples for plasma glucose and insulin will be drawn on Day 5 at –15, 0, 15, 30, 45, 60, 90, 120, 150 and 180 minutes after each meal, for GLP-1 (7-36 amide) and GIP after dinner beginning at 11:45.
- Total urinary glucose excretion over 24 hour
 - On Day 5, urine will be collected in the following time intervals: from pre-dose to 4 hours post-dose, 4 to 8, hours post-dose, 8 to 12 hours post-dose, 12 to 16 hours post-dose, 16 to 20 hours post-dose and 20 to 24 hours post-dose.
- Percent inhibition of renal glucose re-absorption over 24 hours

Revised text:

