For plasma glucose ~~and insulin, GLP-1 (7-36 amide) and GIP~~ the area under the effect time curve until 180 minutes after each meal (AUE_{0-180}) will be calculated. Baseline adjusted geometric mean differences between both treatment groups will be estimated by a linear model on the log-transformed AUEs after each meal and retransforming the point estimates and 95% confidence intervals. **Differences between pre- and post-meal GIP measurements will be determined at dinner only. The change in GIP between the two study periods for each subject will be compared and statistically analyzed.**

The relationship of plasma dapagliflozin concentration vs. percent inhibition of renal glucose re-absorption or urine glucose excretion will be explored.

Section of protocol affected:

Abbreviation list

Previous text:

[...]

AST	Aspartate aminotransferase
$AUC_{ss, (0-24)}$	Area under the plasma concentration versus time curve from time zero to 24 hours at steady state [amount•time/volume]

[...]

$C_{ss,av}$	The average concentration at steady state
C_{max}	Maximum plasma (peak) drug concentration [amount/volume]

[...]

GIP	Glucose-dependent insulinotropic polypeptide
-----	--

GLP-1	Glucagon-like peptide 1
-------	-------------------------

HBsAg	Hepatitis B surface antigen
-------	-----------------------------

[...]

Revised text

[...]

AST	Aspartate aminotransferase
$AUC_{ss, t-t+4}$	Area under plasma concentration-time curve at steady state during each urine collection interval [amount.time/volume]

AUC _{ss, (0-24)}	Area under the plasma concentration versus time curve from time zero to 24 hours at steady state [amount•time/volume]
[...]	
C _{ss,av}	The average concentration at steady state
C_{ss, av, t-t+4}	The average plasma concentration at steady state during each urine collection interval
C _{max}	Maximum plasma (peak) drug concentration [amount/volume]
[...]	
GIP	Glucose-dependent insulintropic polypeptide
GLP-1	Glucagon-like peptide-1
HBsAg	Hepatitis B surface antigen
[...]	

Section of protocol affected:

Section 1.3, Rationale for conduction this study

Previous text:

- To demonstrate that dapagliflozin has a similar pharmacodynamic (PD) effect if dosed twice a day as once a day, as this is how dapagliflozin would be given in a fixed-dose combination with metformin IR

Revised text

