12.2.6 Interim analyses (Not applicable)

Revised heading number:

~~12.2.6~~, 12.2.7 Interim analyses (Not applicable)

Reasons for Amendment:

- To explore the relationship between dapagliflozin plasma concentrations and urine glucose excretion
- Deletion of GLP-1 as PD parameter
- Restricting blood samples for GIP to be taken to only after dinner on Day 5
- Deletion of PK samples Nr. 12 to 21 for BID dosing
- Harmonizing of Section 6.5.1 and Table 3 with regard to blood sampling of GIP and Insulin
- Corrections and harmonisations

Persons who initiated the Amendment:

Astra Zeneca Study Delivery Team Leader

Clinical Study Protocol Amendment No 1

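### Section 12.2.5 makes reporting of the exploratory concentration–effect analysis depend on its own result, with no criterion and no commitment to report a null finding

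*Supplement*

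**What the plan says.** Amendment 1 adds a second exploratory objective, in the synopsis and in Section 2.3: "To explore plasma dapagliflozin concentration vs urine glucose excretion relationship". It is also the first reason listed for that amendment: "To explore the relationship between dapagliflozin plasma concentrations and urine glucose excretion".

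The amendment supplies variables for this purpose. The PK parameter list gains an AUC and an average concentration over each urine collection interval at steady state. Section 11.3 gains a formula for percent inhibition within each 4-hour interval, and the synopsis makes interval percent inhibition and interval glucose excretion outcome variables.

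The amended synopsis states the analysis without condition: "The relationship of plasma dapagliflozin concentration vs. percent inhibition of renal glucose re-absorption or urine glucose excretion will be explored". The new Section 12.2.5 (PK/PD relationship) starts in the same way, "The average plasma concentration vs percent inhibition of glucose re-absorption or the amount of glucose excreted will be explored", but then adds that "the results will be reported separately if any relationship can be determined".

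Amendment 2 does not list Section 12.2.5 among its changes, so this wording is current.

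**The concern.** Whether the answer to a stated objective is reported should not depend on what the answer is. Section 12.2.5 ties the two together and leaves the condition open: it gives no model, estimate or threshold by which a relationship would be judged determined. It also joins the two responses, percent inhibition and glucose amount, with 'or', so the choice of which to pursue is open too.

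Two things follow. A finding of little or no relationship has no reporting commitment behind it. And a relationship that is reported will have passed an undefined filter, so a reader of the report could not tell how it came to be shown.

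The study's rationale is to show similar pharmacodynamic effect for the same daily dose given once or twice a day. The regimens differ in the shape of the concentration profile, so how far interval effect follows interval concentration is relevant background, whether the answer is strong or weak.

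**Working it through.** This is a matter of wording, so the check is to set the passages side by side.

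**1. Reporting of the other analyses.**
- Primary and secondary PD endpoints (Section 12.2.4): "Estimated least square means and difference between treatments least squares means will be reported with 95% confidence intervals". There is no condition on the result.
- Nonparametric analysis (Section 12.2.4): conditional, but on model diagnostics, and given in addition to the ANOVA. The condition concerns assumptions, not the finding.
- PK regimen comparisons (Section 12.2.3): geometric means and ratios with confidence intervals, no condition on the result.
- Concentration–effect relationship (Section 12.2.5): "the results will be reported separately if any relationship can be determined". The condition is the finding.

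**2. Is there a fallback for a null result?** The amended synopsis promises exploration and is silent on reporting. The amended Section 2.3 states the objective only. Neither amendment says where a null result would appear.

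**3. What is produced regardless of Section 12.2.5?**
- Glucose amount per interval: Section 11.3 says it will be reported.
- Interval average concentration: on the amended list of PK parameters to be determined; Section 12.1.2 provides for summaries and listings of PK data.
- Interval percent inhibition: an outcome variable in the amended synopsis, with its formula in the amended Section 11.3.

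So the component series exist whatever happens under Section 12.2.5. Only the analysis that joins them is conditional.

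**4. Size of that analysis.** Section 12.3 plans on 14 completers ("If 14 subjects complete both periods of the study"), each with two periods and six 4-hour urine intervals on Day 5. Pairs per response = subjects × periods × intervals:
- 14 completers: 14 × 2 × 6 = 168.
- All 16 enrolled volunteers complete: 16 × 2 × 6 = 192.

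Both counts assume every interval is evaluable. Each subject contributes up to 12 pairs, so the pairs are not independent.

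**5. Does the plan's precision figure depend on this?** The only stated figure is the ±9.0 percentage points of Section 12.3 for the primary comparison. With within-subject variance 15.4²/2 = 118.58, the standard error is √(2 × 118.58/14) = 4.116. With t(0.975, 12 df) = 2.179, the half-width is 2.179 × 4.116 = 8.97, which agrees with 9.0. Nothing in it depends on Section 12.2.5, and removing the reporting condition leaves it unchanged.

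**The case against.** **'Separately' may be about place.** The sentence can be read as saying that a clear relationship earns its own report, while anything else stays in the clinical study report. That reading is natural, and it stands as a possibility. A reader might go further and infer that a null result will be suppressed; the documents do not say so. They do not say the opposite either, and if the milder reading is meant, one sentence makes it explicit.

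**The data are not lost.** A reader might infer that the paired values vanish if no relationship is seen. Sections 11.3 and 12.1.2 and the amended outcome variables show otherwise. This objection stands in full and confines the point to the linking analysis.

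**The analysis is exploratory.** Also true. Once- versus twice-daily dosing is answered by the comparisons in Sections 12.2.3 and 12.2.4, which Section 12.2.5 does not affect. This lowers the severity but does not justify a result-dependent rule for a stated objective.

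**A flat plot has no simple reading.** Meals at 0, 5 and 12 hours change the filtered glucose load between intervals, so a flat or sloped plot, especially of glucose amount, would not by itself show that the regimens are alike or different. This stands: a null result is relevant context, not proof of similarity.

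**The SAP may settle it.** Section 12.2.1 defers procedures to a SAP that is not among the documents. The choice of model may properly be left there. The reporting condition is different: it is written in the protocol, so it is a statement to correct rather than a detail to await.

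**Conclusion.** The point holds as a low-severity correction. Section 12.2.5, as it stands after both amendments, makes reporting of a stated exploratory objective conditional on its own result, without a criterion and without a commitment for the null case. What is exposed is the reporting of one paired analysis, of 168 to 192 pairs per response under the assumptions shown. The interval data and the primary, secondary and PK regimen comparisons are not exposed.

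A reader might also want to attach a false-positive rate to having two responses to choose from. The plan supports no such figure: it names no test or significance level for this exploration, and the two responses are tied together because the amount excreted is the numerator of percent inhibition.

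The conclusion assumes that no unseen document, the SAP in particular, already promises unconditional reporting. Even then the protocol sentence would need to be brought into line.

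**What to change.** In Section 12.2.5, replace the conditional clause with:

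> Interval-average concentration versus interval percent inhibition and amount of glucose excreted will be plotted and summarised for both regimens, allowing for repeated intervals within subject, and reported in the CSR (or a named separate report) whatever the result.

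This names both responses in place of 'or', fixes which average concentration is meant, and states where the result goes. The form of the model can be left to the SAP.

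The cost is one sentence in the protocol and one figure and one table in the report. Sampling, sample size and the primary analysis do not change.

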12.2.5.1 Adverse events

Revised heading number:

~~12.2.5.1~~, **12.2.6.1** Adverse events

Section of protocol affected:

Section 12.2, Methods of statistical analyses

Previous heading number:

12.2.5.2 ECG

Revised heading number:

~~12.2.5.2~~, **12.2.6.2** ECG

Section of protocol affected:

Section 12.2, Methods of statistical analyses

Previous heading number:

12.2.5.3 Laboratory variables

Revised heading number:

~~12.2.5.3~~, **12.2.6.3** Laboratory variables

Section of protocol affected:

Section 12.2, Methods of statistical analyses

Previous heading number:

12.2.5.4 Vital signs

Revised heading number:

~~12.2.5.4~~, 12.2.6.4 Vital signs

Section of protocol affected:

Section 12.2, Methods of statistical analyses

Previous heading number:

12.2.6 Interim analyses (Not applicable)

Revised heading number:

~~12.2.6~~, 12.2.7 Interim analyses (Not applicable)

Reasons for Amendment:

- To explore the relationship between dapagliflozin plasma concentrations and urine glucose excretion
- Deletion of GLP-1 as PD parameter
- Restricting blood samples for GIP to be taken to only after dinner on Day 5
- Deletion of PK samples Nr. 12 to 21 for BID dosing
- Harmonizing of Section 6.5.1 and Table 3 with regard to blood sampling of GIP and Insulin
- Corrections and harmonisations

Persons who initiated the Amendment:

Astra Zeneca Study Delivery Team Leader

Clinical Study Protocol Amendment No 1

An open-label, randomized, two-period, crossover study to assess the effect of dapagliflozin on percent inhibition of glucose re-absorption when administered once a day (10 mg QD) versus twice a day (5 mg BID) in healthy male and female volunteers

This Clinical Study Protocol and all Amendments to the CSP have been subjected to an internal AstraZeneca peer review.

I agree to the terms of this amendment.

Signature:

This document contains confidential information, which should not be copied, referred to, released or published without written approval from AstraZeneca. Investigators are cautioned that the information in this protocol may be subject to change and revision.

Clinical Study Protocol Amendment

Amendment Number 2
Drug Substance Dapagliflozin
Study Code D1691C00004

Protocol Dated

An open-label, randomised, two-period crossover study to assess the effect of dapagliflozin on percent inhibition of glucose re-absorption when administered once a day (10 mg OD) versus twice a day (5 mg BID) in healthy male and female volunteers

This submission /document contains trade secrets and confidential commercial information, disclosure of which is prohibited without providing advance notice to AstraZeneca and opportunity to object.

Sponsor:

AstraZeneca AB, SE-151 85 Södertälje, Sweden

Centres affected by the Amendment:

The protocol for the study is to be amended as follows:

Changes and additions are highlighted in **bold and underlined**, deleted text as ~~striketrough~~.

Overview of the changes in this Amendment

Section in the protocol affected	Action	Protocol page
Section 3.1, Overall study design and flowchart, 5 th paragraph	Note to type and amount of fluid intake during for Day 1 and Day 5	17
Section 3.1, Overall study design and flowchart, Table 1	Cotinine test added and fasting time before safety lab defined	17f
Section 3.1, Overall study design and flowchart, Table 2	Adjustment of PK sampling times and numbering in BID dosing Day 5, adding safety lab on Day –1	19
Section 4.2, Exclusion criteria 12	Positive cotinine test at enrolment added	25
Section 5.1, Restrictions during the study, bullet 2	Subjects may drink either tap water or non-caloric and non-caffeinated beverages during the study, however at each time interval of both periods the same type of beverage	25f
Section 6.2, Data collection and enrolment	Subjects to be in fasted state for at least 8 hours prior examinations All pregnancy tests will be performed in serum	32
Section 6.21, Follow-up	Subjects to be in fasted state for at least 8 hours prior examinations.	32
Section 6.3.5	Adjustment to reduced blood amount for clinical chemistry Cotinine test added	36 37
Section 7.1	Volume of blood	40

Section of protocol affected:

Section 3.1, Overall study design and flowchart, 5th paragraph

Previous text:

[...]

Breakfast on Day 5 in both periods must be identical; lunch on Day 5 in both periods must be identical; and dinner on Day 5 in both periods must be identical. Healthy volunteers must consume the entire meals within 30 minutes on Day 4 (for practice) and on Day 5. Of each meal on Day 5, approximately 55% of the ingested caloric equivalent should be carbohydrates. The meal schedule for all meals must be identical for all healthy volunteers, and the meal consumption time has to be identical in both periods for each healthy volunteer. Healthy volunteers may not consume caloric beverages between meals or at bedtime, likewise the healthy volunteers are to abstain from liquids with artificial sweeteners' on Day 5.

[...]

Revised text:

[...]

Breakfast on Day 5 in both periods must be identical; lunch on Day 5 in both periods must be identical; and dinner on Day 5 in both periods must be identical. Healthy volunteers must consume the entire meals within 30 minutes on Day 4 (for practice) and on Day 5. Of each meal on Day 5, approximately 55% of the ingested caloric equivalent should be carbohydrates. The meal schedule for all meals must be identical for all healthy volunteers, and the meal consumption time has to be identical in both periods for each healthy volunteer.

On Day 1 and Day 5, the subjects should drink the same liquid and amount with meals.

Healthy volunteers may not consume caloric beverages between meals or at bedtime, likewise the healthy volunteers are to abstain from liquids with artificial sweeteners' on Day 1 and Day 5.

[...]

Section of protocol affected:

Section 3.1, Overall study design and flowchart, Table 1

Previous table:

Table 1 Study Schedule

Assessment	Visit 1 Enrolment	Visits 2^a and 3^b Treatment	Visit 4 Follow-up
Informed consent	✓		
Inclusion/Exclusion criteria	✓	✓	

Assessment	Visit 1 Enrolment	Visits 2^a and 3^b Treatment	Visit 4 Follow-up
Concomitant medication	✓	✓	✓
Medical/Surgical history	✓		
Physical exam	✓	✓ ^c	✓ ^d
Virology screen	✓		
Alcohol urine test	✓	✓	
Demographics	✓		
Drugs of abuse	✓	✓	
12-lead ECG	✓		
Blood pressure and heart rate (including body temperature ^e)	✓	✓	✓
Weight and height ^f	✓		✓
Safety labs (blood and urine) ^g	✓	✓	✓
Randomization ^h		✓	
PK sample collection		✓	
Confinement to unit		✓	
Dapagliflozin dose		✓	
Pregnancy test (serum) ⁱ	✓	✓	
Adverse event questioning		✓	✓
Serious adverse event	✓	✓	✓
Urine sample collections ^k		✓	
Creatinine measurements		✓	
Plasma glucose, insulin, GLP-1 and GIP		✓	

ECG electrocardiogram, GLP glucagon-like peptide, GIP glucose-dependent insulinotropic polypeptide

^a Beginning of period 1.

^b Beginning of period 2

^c Brief history and physical exam

^d To be performed at end of Visit 4 (follow-up)

^e Vital signs will be obtained he volunteer in a supine position (resting in bed for at least 10 minutes)

^f Height will be assessed only at the enrolment visit (Visit 1)

^g Safety labs (blood and urine) will be performed at Visit 1, and upon admission on Day -1 and pre-dose on Day 5, and at Visit 4.

^h Performed at Visit 2 only after all inclusion and exclusion criteria have been satisfied on Day 1.

ⁱ Required for female healthy volunteers only. Serum pregnancy test will be required at Visit 1, on Day -1 of Visits 2 and 3. Healthy female volunteers must have confirmed negative serum pregnancy test from Day -1 of each treatment period prior to receiving the IP

^j AEs will be recorded from first intake of IP in period 1 until follow-up, SAEs will be collected from the time when informed consent is obtained until the end of study (including the follow-up visit).

^k Urine samples for volume, glucose concentration, creatinine concentration.

Revised table

Table 2 Study Schedule

Assessment	Visit 1 Enrolment	Visits 2^a and 3^b Treatment	Visit 4 Follow-up
Informed consent	✓		
Inclusion/Exclusion criteria	✓	✓	
Concomitant medication	✓	✓	✓
Medical/Surgical history	✓		
Physical exam	✓	✓ ^c	✓ ^d
Virology screen	✓		
Alcohol urine test	✓	✓	
Demographics	✓		
Drugs of abuse including cotinine test	✓	✓	
12-lead ECG	✓		
Blood pressure and heart rate (including body temperature ^e)	✓	✓	✓
Weight and height ^f	✓		✓
Safety labs (blood and urine) ^g	✓	✓	✓
Randomization ^h		✓	
PK sample collection		✓	
Confinement to unit		✓	
Dapagliflozin dose		✓	
Pregnancy test (serum) ⁱ	✓	✓	
Adverse event questioning		✓	✓
Serious adverse event	✓	✓	✓
Urine sample collections ^k		✓	
Creatinine measurements		✓	
Plasma glucose, insulin, GLP-1 and GIP		✓	

ECG electrocardiogram, GLP glucagon-like peptide, GIP glucose-dependent insulinotropic polypeptide

^a Beginning of period 1.

^b Beginning of period 2

^c Brief history and physical exam

^d To be performed at end of Visit 4 (follow-up)

^e Vital signs will be obtained the volunteer in a supine position (resting in bed for at least 10 minutes)

^f Height will be assessed only at the enrolment visit (Visit 1)

- ^g Safety labs (blood and urine) will be performed at Visit 1, and upon admission on Day –1 and pre-dose on Day 5, and at Visit 4. **At enrolment and follow-up examination, the subjects should be in fasted state for at least 8 hours, on Day –1 of each period for at least 4 hours. Non-caloric beverages are allowed for the fasting period.**
- ^h Performed at Visit 2 only after all inclusion and exclusion criteria have been satisfied on Day 1.
- ⁱ Required for female healthy volunteers only. Serum pregnancy test will be required at Visit 1, on Day –1 of Visits 2 and 3. Healthy female volunteers must have confirmed negative serum pregnancy test from Day –1 of each treatment period prior to receiving the IP
- ^j AEs will be recorded from first intake of IP in period 1 until follow-up, SAEs will be collected from the time when informed consent is obtained until the end of study (including the follow-up visit).
- ^k Urine samples for volume, glucose concentration, creatinine concentration.

Section of protocol affected:

Section 3.1, Overall study design and flowchart, Table2

Previous table:

Table 2 Study Plan for Each Treatment Period

Visit	Day	Nominal IP protocol time	Blood for PD			Blood for PK		Urine for PD	Other
			Plasma glucose	Plasma creatinine	Insulin, GLP-1, GIP	OD dosing	BID dosing		
	-1	15:30							Check for inclusion and exclusion criteria, drug screen including alcohol.
		Pre-dose				1	1		
	1	00:00	X						Breakfast ^b
		00:15				2	2		
		00:30				3	3		
		01:00				4	4		
		01:30				5	5		
		02:00				6	6		
		03:00				7	7		
		04:00				8	8		
		06:00				9	9		
		08:00				10	10		

Visit	Day	Nominal protocol time	IP	Blood for PD			Blood for PK		Urine for PD	Other
				Plasma glucose	Plasma creatinine	Insulin, GLP-1, GIP	OD dosing	BID dosing		
		12:00	X ^a				11	11		Dinner ^b
		12:15						12		
		12:30						13		
		13:00						14		
		13:30						15		
		14:00						16		
		15:00						17		
		16:00					12	18		
		18:00						19		
		20:00					13	20		
2		24:00	X				14	21		Breakfast ^b
		12:00	X ^a							Dinner ^b
3		Pre-dose					15	22		
		00:00	X							Breakfast ^b
		12:00	X ^a							Dinner ^b
4		Pre-dose			1 (back up sample)		16	23		
		00:00	X							Breakfast ^b
		12:00	X ^a							Dinner ^b
2/3	5	-00:15		1		1				
		Pre-dose			2		17	24	X (start of collection)	Safety lab, vital signs
		00:00	X	2		2			X	Initiation of breakfast ^b
		00:15		3		3	18	25	X	
		00:30		4		4	19	26	X	
		00:45		5		5				

Visit	Day	Nominal protocol time	IP	Blood for PD			Blood for PK		Urine for PD	Other
				Plasma glucose	Plasma creatinine	Insulin, GLP-1, GIP	OD dosing	BID dosing		
		01:00		6		6	20	27	X	
		01:30		7		7	21	28	X	
		02:00		8		8	22	29	X	
		02:30		9		9				
		03:00		10		10	23	30	X	
		04:00		11			24	31	X (end of collection period)	
									X (restart of collection)	
		04:45		12		11				
		05:00		13		12			X	Initiation of Lunch ^b
		05:15		14		13				
		05:30		15		14				
		05:45		16		15				
		06:00		17		16	25	32	X	
		06:30		18		17				
		07:00		19		18			X	
		07:30		20		19				
		08:00		21		20	26	33	X (end of collection period)	
									X (restart of collection)	

Visit	Day	Nominal protocol time	IP	Blood for PD			Blood for PK		Urine for PD	Other
				Plasma glucose	Plasma creatinine	Insulin, GLP-1, GIP	OD dosing	BID dosing		
		09:00		22					X	
		10:00		23					X	
		11:00		24					X	
		11:45		25		21				
		12:00	X ^a	26		22	27	34	X (end of first collection period) X (restart of collection)	Initiation of dinner ^b
		12:15		27		23		35		
		12:30		28		24		36		
		12:45		29		25				
		13:00		30		26		37	X	
		13:30		31		27		38		
		14:00		32		28		39	X	
		14:30		33		29				
		15:00		34		30		40	X	
		16:00		35			28	41	X (end of collection period) X (restart of collection)	
		17:00							X	
		18:00		36				42	X	
		19:00							X	

Visit	Day	Nominal protocol time	IP	Blood for PD			Blood for PK		Urine for PD	Other
				Plasma glucose	Plasma creatinine	Insulin, GLP-1, GIP	OD dosing	BID dosing		
		20:00		37			29	43	X (end of collection period) X (restart of collection)	
		21:00							X	
		22:00							X	
		23:00							X	
	6	24:00		38			30	44	X end of collection period) ^b	

IP investigational product, PK pharmacokinetic, PD pharmacodynamic, GLP glucagon-like peptide, GIP glucose-dependent insulinotropic polypeptide

^a Only in treatment A

^b The IP will be administered together with the meal, which has to be completed within 30 minutes. Regarding the timing of events at mealtime, the following order of activities should be followed: blood sampling for plasma glucose, insulin, GLP-1 and GIP; with meal initiation occurring within 2 min of blood sampling. If the IP is to be administered the following sequence of events should occur: blood sampling, medication administration then meal initiation within 2 min of blood sampling.

Revised table:

Table 2 Study Plan for Each Treatment Period

Visit	Day	Nominal protocol time	IP	Blood for PD			Blood for PK		Urine for PD	Other
				Plasma glucose, Insulin ,	Plasma creatinine	Insulin , GLP-1 , GIP,	OD dosing	BID dosing		
	-1	15:30							Check for inclusion and exclusion criteria, safety lab , drug screen including alcohol.	
		Pre-dose				1	1			
	1	00:00	X						Breakfast ^b	
		00:15				2	2			
		00:30				3	3			
		01:00				4	4			
		01:30				5	5			
		02:00				6	6			
		03:00				7	7			
		04:00				8	8			
		06:00				9	9			
		08:00				10	10			
		12:00	X ^a			11	11		Dinner ^b	
		12:15					12			
		12:30					13			
		13:00					14			
		13:30					15			
		14:00					16			
		15:00					17			
		16:00				12	18			

Visit	Day	Nominal protocol time	IP	Blood for PD			Blood for PK		Urine for PD	Other
				Plasma glucose, Insulin ,	Plasma creatinine	Insulin , GLP-1, GIP,	OD dosing	BID dosing		
		18:00						19		
		20:00					13	20		
	2	24:00	X				14	21	Breakfast ^b	
		12:00	X ^a						Dinner ^b	
	3	Pre-dose					15	22 12		
		00:00	X						Breakfast ^b	
		12:00	X ^a						Dinner ^b	
	4	Pre-dose			1 (back up sample)		16	23 13		
		00:00	X						Breakfast ^b	
		12:00	X ^a						Dinner ^b	
2/3	5	-00:15		1						
		Pre-dose			2		17	24 14	X (start of collection)	Safety lab, vital signs
		00:00	X	2		2			X	Initiation of breakfast ^b
		00:15		3		3	18	25 15	X	
		00:30		4		4	19	26 16	X	
		00:45		5		5				
		01:00		6		6	20	27 17	X	
		01:30		7		7	21	28 18	X	
		02:00		8		8	22	29 19	X	
		02:30		9		9				
		03:00		10		10	23	30 20	X	

Visit	Day	Nominal IP protocol time	Blood for PD			Blood for PK		Urine for PD	Other
			Plasma glucose, Insulin ,	Plasma creatinine	Insulin , GLP-1, GIP,	OD dosing	BID dosing		
		04:00	11			24	31 21	X (end of collection period) X (restart of collection)	
		04:45	12		11				
		05:00	13		12			X	Initiation of Lunch ^b
		05:15	14		13				
		05:30	15		14				
		05:45	16		15				
		06:00	17		16	25	32 22	X	
		06:30	18		17				
		07:00	19		18			X	
		07:30	20		19				
		08:00	21		20	26	33 23	X (end of collection period) X (restart of collection)	
		09:00	22					X	
		10:00	23					X	
		11:00	24					X	
		11:45	25		24 1				

Visit	Day	Nominal protocol time	IP	Blood for PD			Blood for PK		Urine for PD	Other
				Plasma glucose, Insulin ,	Plasma creatinine	Insulin , GLP-1, GIP,	OD dosing	BID dosing		
		12:00	X ^a	26		22	27	34 24	X (end of first collection period) X (restart of collection)	Initiation of dinner ^b
		12:15		27		23		35 25		
		12:30		28		24		36 26		
		12:45		29		25				
		13:00		30		26		37 27	X	
		13:30		31		27 2		38 28		
		14:00		32		28		39 29	X	
		14:30		33		29				
		15:00		34		30		40 30	X	
		16:00		35			28	41 31	X (end of collection period) X (restart of collection)	
		17:00							X	
		18:00		36				42 32	X	
		19:00							X	

Visit	Day	Nominal protocol time	IP	Blood for PD			Blood for PK		Urine for PD	Other
				Plasma glucose, Insulin ,	Plasma creatinine	Insulin , GLP-1 , GIP,	OD dosing	BID dosing		
		20:00		37			29	43 33	X (end of collection period) X (restart of collection)	
		21:00							X	
		22:00							X	
		23:00							X	
	6	24:00		38			30	44 34	X end of collection period) ^b	

IP investigational product, PK pharmacokinetic, PD pharmacodynamic, GIP glucose-dependent insulinotropic polypeptide

^a Only in treatment A

^b The IP will be administered together with the meal, which has to be completed within 30 minutes.

Regarding the timing of events at mealtime, the following order of activities should be followed: blood sampling for plasma glucose, insulin, ~~GLP-1~~ and GIP (GIP only at dinner), with meal initiation occurring within 2 min of blood sampling. If the IP is to be administered the following sequence of events should occur: blood sampling, medication administration then meal initiation within 2 min of blood sampling.

Section of protocol affected:

Section 4.2, Exclusion criteria, Exclusion criteria No. 12

Previous text:

[...]

12. Positive urine drug screen

[...]

Revised text:

[...]

12. Positive urine drug screen **including cotinine**

[...]

Section of protocol affected:

Section 5.1, Restrictions during the study, 2nd bullet

Previous text:

[...]

